4.3 Missing data

Regarding the primary endpoint, the isCGM sensor is wore and collected carefully during MDI therapy or during hospitalization, and thus the probability of missing data associate with primary endpoint remained relatively low. However, if missing data were found, then the percentage of missing data will be reported, the potential patterns of missing data should be examined, and appropriate method should be used for imputation of missing data. The multiple imputation method will be preferred for analyzing the missing data, and the results should be reported in the manuscript as sensitivity analysis.

4.4 Interim analysis

No interim analysis is planned in this study.

5 Statistical analysis

5.1 Data management and general analysis

Electronic dataset system will be used for data collection and management. The data analyses mainly include statistical description and statistical inference. Quantitative data will be described by central tendency and dispersion tendency. The normally distributed data of central tendency and dispersion tendency will be described as means and standard deviation, respectively. The non-normally distributed data of central tendency and dispersion tendency will be described as median and quartiles. The qualitative data will be described as frequency and percentage. Statistical inference, independent *t* test or non-parameter test will be used to compare the quantitative data between the two arms, while chi-square test or Fisher's exact test will be used for comparing the qualitative data between the two arms.

5.2 Analysis of primary endpoints

For the co-primary endpoint comparisons, the statistical analysis will be performed to evaluate the differences between the two groups for the two primary endpoints during MDI therapy. Specifically, the co-primary endpoints used a stepdown strategy designed to maintain type I error at 5% or less for multiple comparisons. The primary endpoint followed no Gaussian distribution, will be presented as median (interquartile range). The mean (95% confidence intervals, CIs) of between-group differences of the median will be calculated by bootstrap method (1000 replications). For the primary efficacy endpoint, non-inferiority will be established if the lower bound of the CI does not less than the noninferiority margin of -7.5%. For the primary safety endpoint, non-inferiority will be established if the upper bound of the CI does not greater than the non-inferiority margin of 2%, which is selected according to previous reports [1][5]. The per-protocol (PP) sets will be also used for sensitivity analysis.

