The study's primary efficacy endpoint is the non-inferiority for percent time spent with sensor glucose level in 3.9-10.0 mmol/L (70-180 mg/dL) between the two study arms. The primary safety endpoint is the percent time spent with sensor glucose level below 3.0 mmol/L (54 mg/dL). For the co-primary endpoint comparisons, the statistical analysis will be performed to evaluate the differences between the two groups during insulin titration period, respectively. Specifically, the mean (95% confidence intervals, CIs) of between-group differences will be calculated. For the

primary efficacy endpoint, non-inferiority will be established if the lower bound of the CI does not less than the noninferiority margin of -7.5%. For the primary safety endpoint, non-inferiority will be established if the upper bound of the CI does not greater than the non-inferiority margin of 2%, which is selected according to previous reports [1][3]. The co-primary end points use a stepdown strategy designed to maintain type I error at 5% or less for multiple comparisons. The secondary endpoints will then be tested in a prespecified order until one of the null hypotheses was non-rejected.

References

北京大学人民医院
PEKING UNIVERSITY PEOPLE'S HOSPITAL

Statistical Analysis Plan: Final

Date: 22 Oct 2022

Study Biostatistician:

[name]

[name]

Research Center of Clinical Epidemiology, Peking University Third Hospital

Study: RCT assessing efficacy and safety of an artificial-pancreas-like closed-loop control in adults with type 2 diabetes on multiple daily injections therapy

Department of Endocrinology and Metabolism

Peking University People's Hospital

[name]

[contact]

[contact]

1 Study aim

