4.1 Population

4.1.1 Sample size

The main study is a randomized controlled trial with noninferiority design. Participants will be assigned 1:1 to either the AP-A arm or the physician arm. We hypothesized that use of the AP-A would not be inferior to physician-guided recommendations in percentage of sensor readings within the target range of 3.9–10 mmol/L. For the sample size calculation, data from the JDRF CGM randomized controlled study and the REPLACE-BG study were used to estimate the properties of the primary endpoint and to define the non-inferiority limit [1][2]. The sample size was calculated using PASS15.0 for non-inferiority analysis, with a margin of 7.5% between arms in a parallel study design with power of 90%, a one-sided significance level of 5% and SD of 13%. Besides, we assume that there is no difference between the two arms in achieving the percentage time of sensor readings within the target range of 3.9–10 mmol/L. The equation for calculating the sample size is as follow [3][4]:

$$n = 2 \frac{(z_{1-\alpha} + z_{1-\beta})^2 S^2}{(\Delta - \delta)^2}$$

In the equation, n is the sample size of each arm, Δ is the non-inferiority margin of the

primary endpoint, δ is the mean difference at which the power is computed, α is the type I error, β is the type II error, and S^2 is the pooled standard deviation of both comparison arms. The resulting analysis showed that 106 subjects were needed for the study. Finally, the study enrolled 119 participants, which met the sample size requirement.

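### Final SAP 5.2 judges time in range (TIR) by a difference of medians, but the SD, margin and 90% power in 4.1.1 belong to a difference of means, and the change of estimator is not listed

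*Supplement*

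**What the plan says.** **Sample size (final SAP 4.1.1).** The trial is sized for TIR (3.9–10.0 mmol/L) "with a margin of 7.5% between arms in a parallel study design". The other design values are 90% power, a one-sided 5% level and an SD of 13%. A true difference of zero is the premise: "we assume that there is no difference between the two arms in achieving the percentage time of sensor readings". The formula uses the pooled SD and a quantity δ that "is the mean difference at which the power is computed". The result is 106 participants; 119 were enrolled.

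**Primary analysis (final SAP 5.2).** The section states: "The primary endpoint followed no Gaussian distribution, will be presented as median (interquartile range". The estimate and 95% CI are then obtained for the between-arm difference of medians by a bootstrap with 1000 replications. Non-inferiority on TIR is declared if the lower limit is not below -7.5%.

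**Original SAP, section 4.** There, "the mean (95% confidence intervals, CIs) of between-group differences will be calculated", with the same -7.5% limit and no mention of medians or a bootstrap.

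**Summary of changes for the SAP.** It lists changes to secondary endpoints, the analysis of physician overrides, and graphics. It does not mention the primary estimator.

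**The concern.** Sections 4.1.1 and 5.2 of the same final SAP concern two different quantities. The SD of 13 gives the standard error of a mean directly. The standard error of a median depends on the density of TIR near its centre, which the SD does not fix. The power statement therefore does not carry over.

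The margin does not carry over automatically either. If the algorithm shifts every participant's TIR by the same amount, the mean and median differences are equal. If it affects only some participants, they can diverge. In a non-inferiority trial of a dosing algorithm, the divergence that matters is a loss confined to participants who are already poorly controlled, because a median can be blind to it.

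Non-normality, the only reason 5.2 offers, does not by itself rule out a comparison of means with about 60 participants per arm.

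**Working it through.** **Inputs (final SAP 4.1.1 unless noted).** Margin 7.5; SD 13; one-sided alpha 5%; power 90%; true difference 0; 1:1 allocation; calculated N 106; enrolled N 119 (59.5 per arm on average). Decision rule: 95% CI against -7.5 (5.2). The shape of TIR is not given and has to be assumed.

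**1. The plan's own figure.** n per arm = 2(1.645 + 1.282)² × 13² / 7.5² = 51.5, so 52 per arm or 104. With the t distribution, power is 89.9% at 52 per arm and 90.4% at 53 per arm. Hence 53 per arm, or 106: the stated figure reproduces, and it is for means.

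**2. Standard errors at N = 119.**
- Means: 13 × √(2/59.5) = 2.38.
- Medians, normal data: multiply by √(π/2) = 1.253, giving 2.99.

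**3. Power for normal TIR**, as Φ(7.5/SE − z), with z = 1.960 for the 95% CI rule and 1.645 for one-sided 5%:

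| Estimator | N | 95% CI rule | One-sided 5% |
|---|---|---|---|
| Means | 119 | 88.2% | 93.3% |
| Medians | 119 | 70.9% | 80.7% |
| Means | 106 | 84.4% | 90.7% |
| Medians | 106 | 65.9% | 76.6% |

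Example: medians, N = 119, 95% CI: 7.5/2.99 = 2.51; 2.51 − 1.96 = 0.55; Φ(0.55) = 0.71.

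**4. N for 90% power with medians, normal TIR.** 51.5 × π/2 = 80.8, so 81 per arm (162 in total) at one-sided 5%. With the 95% CI rule, 100 per arm (200 in total). Both are before dropout.

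**5. Dependence on shape.** Simulated bootstrap 95% CI with 1000 replications, 60 and 59 participants, SD 13, true difference 0:

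| Assumed shape of TIR | Power, medians | Power, means |
|---|---|---|
| Normal | 69% | 87% |
| Beta on 0–100, mean 60, 70 or 80 | 66–70% | 88–90% |
| Skewed (gamma) | 79% | 89% |
| t with 5 df | 86% | 88% |
| Laplace | 96% | 89% |
| Uniform | 43% | 88% |

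Allowing for simulation error and small differences between runs, about 64–70% is a fair range for medians under the beta shapes. Power for means stays at about 87–90% whatever the shape.

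**6. What a median can miss.** Suppose the lowest 30% of AP-A participants each lost 25 points of TIR and no one else changed. Mean TIR would fall by 0.30 × 25 = 7.5, the whole margin. Those participants were below the median before and remain below it, so the median difference would be 0.

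**The case against.** **The loss cannot be fixed at one figure.** The 71% rests on normal data, while 5.2 says that TIR is not Gaussian. With heavy tails the median equals or beats the mean. This stands, so 71% is one conditional value within a range. Bounded beta shapes, a natural choice for a percentage, nevertheless give values close to it.

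**The median does not account for the whole fall from 90% to 71%.** A reader might infer that it does. Part comes from a separate mismatch: sizing at one-sided 5% but testing with a 95% CI. At the planned alpha and N = 119, medians give 81% and means 93%. Under the CI rule the like-for-like comparison is 71% with 88%.

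**The margin argument and the power figure need different conditions.** If TIR is normal in both arms, mean and median coincide and -7.5 serves both. The margin problem arises when the arms differ in shape. The documents also do not say on which scale the two cited studies supported 7.5; they only use it in a formula for means. This stands as a limit. What remains is that no justification on the median scale is given.

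**A data-driven choice is not shown.** The past tense in 5.2 and the report of 119 enrolled invite that inference. However, the documents mix tenses throughout, complete enrolment does not mean that results by arm were known, and final SAP 2.3 masks statisticians to allocation. Section 5.1 also allows non-parametric methods in general. The choice may have followed sight of the data, but the text does not establish it. What it does establish is an unlisted change.

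**Bootstrap noise is minor.** For normal TIR, 1000 replications give a Monte Carlo SE of about 0.25 points on the limit, roughly 3% of the margin. That does not undermine the analysis.

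**Low power does not create false claims.** Correct: loss of power raises the risk of failing to show non-inferiority. The risk on the other side comes only from the tail problem in step 6.

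**Conclusion.** The point holds as a mismatch within the final SAP. The primary test is on medians, the sample size and 90% power are for means, the margin is reused without support on the median scale, and the change of primary estimator is missing from the summary of changes. None of this needs a distributional assumption.

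The size does need one. With SD 13, a true difference of 0, all 119 analysed and the 95% CI rule, power for medians is about 71% if TIR is normal and about 64–70% for beta shapes; the shapes tried span 43% to 96%. Power for means is about 88% under the same rule.

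That the original SAP meant a difference of arm means is the natural reading of its text, though it does not say so expressly.

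**What to change.** 1. In 5.2, make the difference in mean TIR (AP-A minus physician) the primary estimate. Take its CI from a model with robust standard errors or from a participant-level bootstrap of means, and judge the lower limit against -7.5.
2. Keep the median difference as a sensitivity analysis and median (IQR) as description.
3. State the CI level that matches the planned alpha, so that 4.1.1 and 5.2 agree.
4. Record the change of primary estimator in the summary of changes, with its date, its reason and what data had been seen.
5. If medians are kept as primary, restate the power under named shapes and justify -7.5 on the median scale.

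More bootstrap draws and a fixed seed are optional good practice.

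**Cost.** A few lines of SAP text and a short re-run. The drawback is that one change to the SAP after enrolment has to be explained; reporting both estimates side by side limits that.

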- When the recommended insulin dosages are greater than actual administered ones, the percent time spent with sensor glucose in 3.9-10.0 mmol/L within 4 hours after insulin injection will be compared with the circumstances consistent with physician decisions in the AP-A arm and that in the physician arm using Mann-Whitney U test, respectively.
- When the recommended insulin dosages are greater than actual administered ones, the sensor glucose at 4 hours after insulin injection will be compared with the circumstances consistent with physician decisions in the AP-A arm and that in the physician arm using Mann-Whitney U test, respectively.
- When the recommended insulin dosages are less than actual administered ones, the percent time spent with sensor glucose in 3.9-10.0 mmol/L within 4 hours after insulin injection will be compared with the circumstances consistent with physician decisions in the AP-A arm and that in the physician arm using Mann-Whitney U test, respectively.
- When the recommended insulin dosages are less than actual administered ones, the sensor glucose at 4 hours after insulin injection will be compared with the circumstances consistent with physician decisions in the AP-A arm and that in the physician arm using Mann-Whitney U test, respectively.

5.4 Graphical analysis

To clearly present the between-arm differences of the endpoints, a forest plot will also be provided for the isCGM derived endpoints. Besides, a comparison plot of isCGM glucose pattern between the two arms during the study period will also be presented, where the hypoglycemia events (< 3.0 mmol/L (54 mg/dL)), median, areas enclosed by 25%-75% and 5%-90% quantiles of sensor glucose level of each arm will be plotted. Finally, to compare the insulin dosage recommended by AP-A with the actual executed dosage, a Bland-Altman plot of the agreement between proposed and actual administered insulin dosage will be provided, together with a plot of the differences between proposed and actual administered insulin dosage during the titration period for each participant, where the differences between proposed and actual administered insulin dosage will be represented as dots, and the sizes of the dots will be proportional to their frequency. Besides, the median line (smoothed) of differences during the titration period will also be provided. Finally, the zone enclosed by the

10% and 90% quartile lines (smoothed) of the differences during the titration period will also be presented, and the number of the differences in each titration day will be identified in the plot. The pseudo-codes for the aforementioned plots are provided as follows:

Algorithm 1 Pseudo-code of the forest plot using R

Require: Data of the isCGM derived endpoints for each arm, data of the between-arm differences (mean (95% CIs)) of the isCGM derived endpoints

Ensure: A forest plot for the isCGM derived endpoints

- 1: Read data as $fp \leftarrow \text{read.csv}(\text{"data address"})$ in R
 - 2: Determine the style of forest plot $Data \leftarrow \text{fpShapesGp}(\text{lines}, \text{box})$ in R
 - 3: Output forest plot $\leftarrow \text{forestplot}(fp, \text{options}, \text{style})$ in R
 - 4: return
-

Algorithm 2 Pseudo-code of the comparison plot of isCGM glucose pattern between the two arms using Matlab

Require: isCGM data files for the two arms

Ensure: Comparison plot of isCGM glucose pattern between the two arms

- 1: for each file in the AP-A arm do
 - 2: Get isCGM data
 - 3: Get isCGM data sampling time
 - 4: for $i = 1$ to the length of isCGM data
 - 5: if i th isCGM data < 54 mg/dL
 - 6: $n_a \leftarrow n_a \cup i$ th isCGM data sampling time
 - 7: end
 - 8: Determine the location of i th isCGM data in the day (24h) according to its sampling time
 - 9: Fill the NaN value in the location of vacant isCGM data in the day
 - 10: Get daily isCGM data in chronological order stored in the rows of a matrix φ
 - 11: end
 - 12: $\varphi_a \leftarrow \varphi_a \cup \varphi$
 - 13: end
 - 14: for each file in the physician arm do
 - 15: Get isCGM data
 - 16: Get isCGM data sampling time
 - 17: for $i = 1$ to the length of isCGM data
 - 18: if i th isCGM data < 54 mg/dL
 - 19: $n_b \leftarrow n_b \cup i$ th isCGM data sampling time
 - 20: end
 - 21: Determine the location of i th isCGM data in the day (24h) according to its sampling time
 - 22: Fill NaN value in the location of vacant isCGM data in the day
 - 23: Get daily isCGM data in chronological order stored in the rows of a matrix φ
 - 24: end
 - 25: $\varphi_b \leftarrow \varphi_b \cup \varphi$
 - 26: end
 - 27: Compute median, 5%, 25%, 75% and 90% quartile values of sensor glucose level in the day for AP-A arm using φ_a
 - 28: Compute median, 5%, 25%, 75% and 90% quartile values of sensor glucose
-

- level in the day for physician arm using φ_b
- 29: Plot areas enclosed by 25%-75% and 5%-90% quartile lines of sensor glucose level in the day for AP-A arm, respectively
 - 30: Plot a median line of sensor glucose level in the day for AP-A arm
 - 31: Plot hypoglycemia events for AP-A arm using n_a
 - 32: Plot areas enclosed by 25%-75% and 5%-90% quartile lines of sensor glucose level in the day for physician arm, respectively
 - 33: Plot a median lines of sensor glucose level in the day for physician arm
 - 34: Plot hypoglycemia events for physician arm using n_b
-

Algorithm 3 Pseudo-code of Bland-Altman plot using Matlab

Require: Data of the differences between proposed and actual administered insulin dosage

Ensure: A Bland-Altman plot of the agreement between proposed and actual administered insulin dosage

- 1: Compute the mean value m of the differences
 - 2: Compute the standard deviation value SD of the differences
 - 3: Compute upper value of 95% limits of agreement using $m+1.96SD$
 - 4: Compute lower value of 95% limits of agreement using $m -1.96SD$
 - 5: for each difference do
 - 6: if difference $< m+1.96SD$ && difference $> m -1.96SD$
 - 7: $n \leftarrow n + 1$
 - 8: end
 - 9: end
 - 10: Compute the proportion of the differences falling in the limits using n
 - 11: Plot the differences as dots
 - 12: Plot a mean line of the differences
 - 13: Plot lines of 95% limits of agreement
-

Algorithm 4 Pseudo-code of the plot of differences between proposed and actual administered insulin dosage during the titration period for each participant using Matlab

Require: Data of the differences between proposed and actual administered insulin dosage during the titration period for each participant

Ensure: A plot of differences during the titration period for each participant

- 1: Determine the longest titration period among all the participants
 - 2: Generate a $n \times N$ matrix φ that stores all the differences; n is the number of the participants and N is the longest titration period
 - 3: for each participant do
 - 4: Store the differences of each participant in the row of φ
 - 5: Fill the value of NaN in the location of vacant differences
 - 6: end
 - 7: for $i = 1$ to N do
 - 8: Count the number of the kind of difference and the number of each kind of differences in $\varphi(:, i)$
 - 9: Plot each kind of differences at abscissa i as a dot whose size is proportional to its number
 - Count the number of the total differences in each titration day
 - 10: end
 - 11: Compute median, 10%, and 90% quartile values of the differences during the titration period using φ
-

12: Plot a median line (smoothed) of the differences

13: Plot areas enclosed by 10%-90% quartile lines (smoothed) of the differences

14: Identify the number of the differences in each titration day

5.5 Software and significant level of the statistical analyses

The statistical analyses for baseline characteristics of participants will be conducted using SPSS, version 27 (IBM Software). Other statistical analyses will be performed using MATLAB 2017b (Mathworks, Inc., Natick, MA) for Windows and R, version 4.2.1 (R Foundation for Statistical Computing). Statistical significance is set as $P < 0.05$ with two-sided testing. All plots will be generated by the MATLAB 2017b (Mathworks, Inc., Natick, MA), except for the forest plot, which will be provided using R, version 4.2.1.

References

4. Julious Steven A. Tutorial in Biostatistics. Sample sizes for clinical trials with Normal data. *Statistics in Medicine*. 2004; 23:1921-1986.

Summary of Changes for Statistical Analysis Plan

[1] Amendments at secondary endpoints after the study

One of the secondary endpoints, glycated albumin (GA) level at the last visit was not included in the of the final analysis, since GA was not obtained from more than half of the participants due to frequent partial lock-down because of COVID-19 during the study period in Beijing.

Meanwhile, to further explore the safety of the algorithm, an additional secondary endpoint was included in the final statistical analysis plan. In the intervention group, if physician overrides occurred, the sensor glucose level at 4 hours after insulin injection.

[2] Amendments at the analysis of physician overrides

To further explore the performance of the algorithm, the dosages suggested by AP-A will be divided into three categories: in consistent with physician approval, greater than actual administered dosage, and less than actual administered dosage. The percent time spent with sensor glucose in 3.9-10.0 mmol/L within 4 hours after insulin injection, and sensor glucose at 4 hours after insulin injection will be calculated in each category and the physician arm. If the outcomes do not follow Gaussian distribution, they will be presented as median (interquartile range) and tested by Mann-Whitney U test.

[3] Graphical analysis

To clearly present the between-arm differences of the endpoints, a forest plot will be provided for the isCGM derived endpoints. Besides, a comparison plot of isCGM glucose pattern between the two arms during the study period will also be presented, in which the hypoglycemia events (< 3.0 mmol/L (54 mg/dL)), median, 25%-75% and 5%-90% sensor glucose level of each arm will be plotted. Finally, to compare the insulin dosage recommended by AP-A with the actual executed dosage, a Bland-Altman plot of the agreement between proposed and actual administered insulin dosage will be presented, together with a plot of the differences between proposed and actual administered insulin dosage during the titration period for each participant.
